14 STATISTICAL CONSIDERATIONS

14.1 Introduction

All baseline, primary and secondary outcome measures will be reported using appropriate summary statistical measures. There are no formal hypotheses evaluated in this study.

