14.2 Sample Size

A sample size of 30 has been estimated for this feasibility study. As this is a feasibility study, the sample size calculation can be difficult to determine.

Hertzog 2008 [38] recommends a sample size of between 20 and 40 patients for feasibility studies involving group comparisons. Hertzog suggests 30-40 patients per group will be required to yield confidence intervals whose lower limits can help define the range of plausible values for a subsequent power analysis.

Whitehead et al. 2016 [39] produced methods of calculating the optimal solution and approximate rules. For a main trial designed with 90% power and two-sided 5% significance, Whitehead et al. recommends a feasibility trial sample size per treatment arm of 75, 25, 15 and 10 for standardised effect sizes that are ≤0.1 (extra small), 0.2 (small), 0.5 (medium) and 0.8 (large) respectively.

The results of this feasibility study of 30 patients (single arm) will serve as data for sample size calculations for a further study. There are ethical and economic reasons for keeping this study population small, however the study results need to provide enough information to fulfil the specified primary and secondary endpoints.

With these reasons in mind and the recommendations of the two reference papers above, a sample size of 30 patients will be used for the INCA feasibility study.

The main outcome that will contribute to data for subsequent studies will be based on changes in pain intensity as measured by NRS (see Section 9). Feasibility data regarding the potential effects of Anakinra on pain intensity will be used to inform the sample size for the next stage of the study. The primary outcome of safety (throughout the study) and recruitment will be used to assess the rationale and feasibility of performing a larger RCT.

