14.4.1 Patient Groups for Analysis

Full Analysis Set

In order to follow the Intention To Treat (ITT) principle this will consist of all eligible and registered participants at baseline (0 day), excepting for: a) participants withdrawing consent between baseline (0 day) and starting therapy; b) participants withdrawn from the study after baseline (0 day) because of irregularities with the consent process; c) participants whose information determining ineligibility existed before registration but was not read until after registration.

Safety Set

All participants who received at least one dose of the trial treatment.

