#### 22 Analysis Datasets

#### 22.1 Efficacy Analyses

The primary and secondary outcome analyses will be conducted on all registered participants and for whom the outcome(s) of interest have been observed/measured. Patients who withdrew consent for trial continuation will contribute outcome data up until the point of withdrawal unless the patients' specifically request that the data are not to be used. No imputations will be made.

The membership of the analysis set for each outcome will be determined and documented and reasons for participant exclusion will be given prior to analysis. Reasons may include missing data, loss to follow up.

A per protocol analysis will not be performed, instead the occurrence of each protocol deviation will be monitored and sensitivity analysis performed as appropriate with patients experiencing deviations

of concern removed. The sensitivity analysis will apply to a secondary analysis of the primary outcome only.

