#### 22.2 Safety Analyses

The safety analysis data set will contain all participants that are registered and commenced trial treatment (received at least one dose of Anakinra).

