#### 25.2.2.1 Derivation

This is defined as the proportion of patients with no serious or condition-specific AEs. Pre-determined potential condition-specific AEs are:

- Persistent pain at injection site (greater than 1 week) of at least moderate intensity (≥5 on a 0-10 NRS scale)
- Increase in CRPS associated pain (≥ 2points NRS), ongoing for >1 month.

Serious or condition-specific AEs are indicated on the following case report forms (CRFs) INCA Premature discontuation form, INCA Withdrawal form, Form 6: Follow up, Form 5: Telephone follow up and Form 7: Final telephone follow up. Further details of the events are collected on INCA Adverse Events form and INCA Serious safety event report form.

Patients will be classified as either having experienced at least one serious or condition-specific AE or experienced no serious or condition-specific AEs. The proportion of patients with no serious or condition-specific AEs will be defined as:

[total number of patients to have experienced no serious or condition-specific AEs]/[total number of registered patients].

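### SAP 25.2.2.1 and 22.1 define the primary safety proportion differently, and a registered patient never dosed or lost early can be counted as event-free

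*SAP*

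**What the plan says.** The primary outcome is the proportion of patients with neither a serious nor a condition-specific adverse event. The condition-specific events are injection-site pain lasting more than 1 week and a CRPS pain increase lasting more than 1 month. Protocol section 9, Table 3 sets the evaluation window at baseline to day 180.

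The documents contain four statements about who belongs in the analysis:

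- **SAP 25.2.2.1** gives the ratio "total number of patients to have experienced no serious or condition-specific AEs]/[total number of registered patients" and the rule "Patients will be classified as either having experienced at least one serious or condition-specific AE or experienced no serious or condition-specific AEs". There is no class for a patient who could not be assessed.
- **SAP 22.1**, headed as efficacy analyses, says: "The primary and secondary outcome analyses will be conducted on all registered participants and for whom the outcome(s) of interest have been observed/measured". It allows no imputation, and on exclusions it adds: "Reasons may include missing data, loss to follow up". Patients who withdraw contribute data up to withdrawal.
- **SAP 22.2** says: "The safety analysis data set will contain all participants that are registered and commenced trial treatment (received at least one dose of Anakinra". Protocol 14.4.1 has an equivalent safety set. Neither is tied to the primary outcome.
- **Protocol 14.4.1** removes from the full analysis set "participants withdrawing consent between baseline (0 day) and starting therapy". The SAP does not repeat this exclusion.

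SAP 19 also foresees registered patients who are excluded from the primary analysis. The ratio in 25.2.2.1 has no place for them.

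**The concern.** Two statisticians could each follow the SAP and report different headline figures. One would divide by everyone registered. The other would first drop patients judged unobserved.

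The literal reading of 25.2.2.1 has a direction. A registered patient with no recorded event falls into the no-event class however short the exposure or follow-up. Yet the CRPS pain event needs more than 1 month to be shown, and the SAP's own derivation of pain increase (25.1.2.2, progression criteria) applies only after day 30. Someone lost in week 2 cannot have shown that event.

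SAP 22.1 does not settle the matter. It keeps data up to withdrawal and sets no minimum follow-up, so a patient who is dosed, event-free and gone in week 2 could be called observed under both sections. Protocol 14.2 says the primary safety outcome will help to judge whether a larger trial is warranted, so its denominator should not be left to be chosen once drop-out is known.

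**Working it through.** **The plan's own figure.** There is none to reproduce for this proportion. Protocol 14.2 says "A sample size of 30 has been estimated for this feasibility study", based on pilot-study guidance, with no event rate or precision for the safety proportion. Protocol 14.1 says "There are no formal hypotheses evaluated in this study".

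**Inputs.** N = 30 (Protocol 14.2). Let e be the number of patients with an event, and m the number never dosed or lost early with no recorded event. The documents give neither. Assumed ranges: e = 0, 3, 6 or 9, and m = 0 to 6.

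**Three readings.**

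- A: the m patients count as event-free: (30 − e)/30.
- B: the m patients are excluded: (30 − m − e)/(30 − m).
- C: the m patients stay in the denominator but are not credited as event-free: (30 − m − e)/30.

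The shift from B to A is

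A − B = e/(30 − m) − e/30 = e·m / [30(30 − m)].

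It is never negative, and it is zero when e = 0 or m = 0.

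| e | m | A | B | A − B (points) | C |
|---|---|---|---|---|---|
| 3 | 3 | 27/30 = 90.0% | 24/27 = 88.9% | 1.1 | 24/30 = 80.0% |
| 3 | 6 | 27/30 = 90.0% | 21/24 = 87.5% | 2.5 | 21/30 = 70.0% |
| 6 | 3 | 24/30 = 80.0% | 21/27 = 77.8% | 2.2 | 21/30 = 70.0% |
| 6 | 6 | 24/30 = 80.0% | 18/24 = 75.0% | 5.0 | 18/30 = 60.0% |
| 9 | 3 | 21/30 = 70.0% | 18/27 = 66.7% | 3.3 | 18/30 = 60.0% |
| 9 | 6 | 21/30 = 70.0% | 15/24 = 62.5% | 7.5 | 15/30 = 50.0% |

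Check of the largest shift: 9 × 6 / (30 × 24) = 54/720 = 0.075.

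**Scale.** Exact (Clopper-Pearson) 95% intervals at N = 30 are 50.6% to 85.3% for 21/30 and 61.4% to 92.3% for 24/30. Every shift in the table is small beside them.

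**A − B is a difference between readings, not a bias against the truth.** When the m patients were followed for part of the window, B is too low, because it keeps early events and drops event-free time. A stylised case shows this: true event risk 20% over 180 days at constant hazard, and half the patients lost at day 90. The half-lost figure is chosen only to make the effect visible.

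- Recorded event risk: 0.5 × 0.20 + 0.5 × (1 − √0.8) = 0.100 + 0.053 = 0.153.
- Crude event-free proportion (A): 1 − 0.153 = 84.7%, which is 4.7 points above the true 80%.
- Restricted to patients with an event or full follow-up (B): 0.40/(0.40 + 0.153) = 72.4% before rounding of the 0.153, which is 7.6 points below.

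So simply excluding everyone with incomplete follow-up is not a safe repair. An estimate that uses the partial follow-up is needed.

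**The case against.** A reader might infer that the plan knowingly counts untreated and lost patients as safe, and that the headline must therefore be inflated, perhaps heavily, since the progression criteria accept half of participants not completing treatment. The documents do not support that.

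- **Other sections favour exclusion.** SAP 22.1 limits the analysis to observed outcomes and names missing data and loss to follow-up as reasons to exclude. Protocol 14.4.5 plans complete-case analysis. SAP 19 reports exclusions from the primary analysis with reasons. What is established is a conflict, not a decision to count these patients as safe.
- **The direction is not fixed.** The shift is nil without events or without such patients, and reading C lowers the figure.
- **The never-dosed group is probably small.** Participants are registered after baseline assessments and taught to inject the same day (Protocol 10.5 and 10.6).
- **Stopping treatment is not loss to follow-up.** The 50% criterion in Protocol section 11 concerns completion of active treatment. Protocol 10.9 continues assessments after anakinra is stopped and follows adverse events to day 180. Withdrawals due to an adverse event are followed until it resolves or the participant is stable, and the withdrawal and discontinuation forms feed the primary outcome.
- **Attrition will be visible.** Withdrawals are listed with days in the trial, and retention at days 120 and 180 is reported.

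All of this stands, and it limits the size of the problem. It does not remove it. Participants may leave without giving a reason, and a lost participant is by definition out of contact. The sensitivity analysis in SAP 25.2.2.2 covers protocol deviations of concern and is not stated to cover incomplete follow-up. No interval or bound is planned for the primary proportion.

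**Conclusion.** The point holds as a moderate one. SAP 25.2.2.1 and 22.1 give different denominators for the primary outcome, neither says when an absence of events counts as observed, and the at-least-one-dose set is not used for a primary outcome that concerns safety. A patient never dosed or lost early can therefore be counted as event-free. Against exclusion this moves the result up by 0 to 7.5 points, under the assumed range of up to 6 such patients and up to 9 with events among 30.

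Early loss is the main concern, and moving to the safety set alone does not cure it, because those patients were dosed. Certain inflation, or a large one, is not shown. The severity is limited further because the study is descriptive and tests no hypothesis on this proportion.

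**What to change.** Amend the SAP before the final analysis:

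1. Name the safety set (at least one dose) as the denominator in 25.2.2.1, and change 22.1 to agree.
2. Define the follow-up needed for an observed absence of events. The day-180 completion rule already in SAP 25.2.3.1.1 could serve.
3. Report the number of dosed patients with incomplete follow-up and no event, and separately the number registered but never dosed.
4. Beside the crude proportion, give a Kaplan-Meier event-free estimate at day 180 with a confidence interval. State the event date used, and state the assumption that censoring is non-informative, which may be doubtful if patients leave because of pain.
5. Add a worst-case bound that counts incomplete follow-up as not event-free (reading C, with the safety set as denominator).
6. Do not make the proportion among patients with an event or full follow-up the main estimate, since it is biased downward.

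The cost is a few lines of SAP text and one short table. No new data are needed. The headline may become slightly less favourable.

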#### 25.2.2.2 Analysis

The proportion of patients with no serious or condition-specific AEs will be reported. For participants who experience at least one serious or condition-specific AE the total number and average number per participant of the following will be reported:

- serious AEs
- condition-specific AEs
- serious and/or condition specific AEs

A sensitivity analysis will be performed on the primary outcome to remove patients experiencing protocol deviations of concern from the analysis set. The protocol deviations of concern will be identified and agreed prior to final analysis.

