9 OUTCOMES

Primary Outcome

The proportion of patients with no serious or condition-specific AE's. Pre-determined potential condition-specific AE's include persistent pain at injection site (greater than 1 week) of at least moderate intensity (5 or greater on a 0-10 NRS scale) and increase in CRPS associated pain (>=2points NRS), ongoing for >1 month.

Secondary Outcome(s)

To identify any barriers to patient recruitment and retention:

- 1. Monthly registration rate.
- 2. The proportion of patients completing the study retention rate, and reasons for non-completion.

To obtain data that will enable a larger RCT to be designed in the future:

- 3. Change of pain intensity measured on a 0-10 point NRS from baseline (0 day) to 4 months/120 days after completion of Anakinra administration. Pain intensity at 120 days is defined for the purpose of this study a mean of the weekly scores and daily over the last month of drug administration. This is determined by calculating the results of the patient pain diaries.
- 4. CRPS severity score
- 5. Global Impression of change
- 6. Analgesic Medication use
- 7. EQ-5D 5L
- 8. Patient Health Questionnaire 9 (PHQ-9)
- 9. Brief Pain Inventory (BPI)
- 10. Hospital Anxiety and Depression Scale (HADS)
- 11. Skin sensitivity measured by mechanical quantitative sensory testing (QST)
- 12. Limb Volume (Figure of 8)
- 13. Work status

Table 3: Timepoints for objectives and outcome measurements

Objectives	Outcome Measures	Timepoint(s) of evaluation
To determine the safety/tolerability of Anakinra	Proportion of patients without SAEs	Baseline (0 day) -180 days
To identify barriers to recruitment and	Monthly registration rate	Baseline (0 day)
retention	Retention rate (proportion of patients completing study) and reasons for non-completion	Day 120/180
To obtain data that will enable a larger RCT to be designed in the future	Change of pain intensity measured on a 10-point NRS	Baseline (0 day) – day 120
	CRPS Severity Score	Baseline (0 day), 30, 60, 90, 120 days
	Global Impression of change (PGIC)	Day 120
	Change in Pain Interference measures: PHQ-9, BPI and HADS	Baseline (0 day), 30, 60, 90, 120 days
	EQ5D-5L	Baseline (0 day), 30, 60, 90, 120 and 180 days
	Skin sensitivity measured by Mechanical QST	Baseline (0 day) and day 120
	Limb volume (by figure of 8)	Screening visit, 60 day and 120 days
	Work status	Baseline (0 day) and day 120
	Analgesic Medication use	Baseline (0 day) and day 120

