#### 16 Sample size calculation

A sample size of 30 has been estimated for this feasibility study. As this is a feasibility study, the sample size calculation can be difficult to determine. The results of the feasibility study will serve as data for sample size calculations for a further study. Additional details and references for the selected sample size are provided in the "Sample size" section of the protocol.

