25.2.3.2.11 Work status

25.2.3.2.11.1 Derivation

Work status is recorded at baseline and day 120, with the following categories:

Employed

Self-employed

Not working.

25.2.3.2.11.2 Analysis

Categorical data will be summarised using frequencies and percentages at baseline and day 120 with

the denominator being those who completed the question at each timepoint.

To compare work status at baseline and day 120 a cross-tabulation will be provided with two

percentages using the denominators of total number of patients in the work status category at

baseline and at day 120 i.e. row and column percentages. A simiplified table of working (classified as

employed or self-employed) and not working at baseline and day 120 will also be provided.

26 Safety Evaluations

All non-serious adverse events (AEs) and SAEs reported by the clinical investigator will be presented

in a table (or non-serious adverse reactions (ARs) and SARs if the study does not capture unrelated

AEs). The number (and percentage) of patients experiencing each AE/SAE will be categorised by

severity (mild, moderate, severe). For each patient, only the maximum severity experienced of each

type of AE will be displayed. The number (and percentage) of occurrences of each AE/SAE will be

presented. No formal statistical testing will be undertaken.

27 Additional Analyses

No additional analysis planned.

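### SAP 25.2.2.2 averages SAEs and pain events over anyone with either kind, and no final output counts the distinct patients with each

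*SAP*

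**What the plan says.** SAP 25.2.2.1 sorts participants on the composite alone: "Patients will be classified as either having experienced at least one serious or condition-specific AE or experienced no serious or condition-specific AEs". The headline figure is the ratio "total number of patients to have experienced no serious or condition-specific AEs]/[total number of registered patients".

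SAP 25.2.2.2 reports that proportion and then describes what lies behind it: "For participants who experience at least one serious or condition-specific AE the total number and average number per participant". Three items follow: serious AEs, condition-specific AEs, and the two together. Read as written, the same set of participants is the denominator for all three averages.

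Three other places bear on the point:

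- **SAP 26 (Safety Evaluations):** "The number (and percentage) of patients experiencing each AE/SAE will be categorised by" severity, using each patient's worst grade for each type of event. Occurrences of each type are counted separately.
- **SAP 25.1.2.2 (progression criteria):** the number and proportion of registered participants with each of the two pain events and with a serious adverse reaction (SAR), for interim review.
- **Protocol 9, Table 3:** against the safety and tolerability objective, from baseline to day 180, the measure listed is "Proportion of patients without SAEs". The SAP has no matching derivation.

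**The concern.** The composite joins two very different things: serious events such as hospital admissions, and pain at the injection site or in the affected limb. Protocol 14.2 says the safety outcome will help to decide whether a larger RCT is justified. A reader will therefore want to know how much of the composite is serious events and how much is pain, counted in patients.

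The summaries placed beside the primary result do not answer that. Whether a patient enters the SAE denominator depends partly on whether that patient had pain. Two cohorts with the same SAEs can show different SAE averages, and cohorts with different numbers of SAE patients can show the same one. With a single arm of 30 and no comparator, the descriptive breakdown is what the reader has to go on.

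**Working it through.** **Inputs.** The documents supply the denominator of the averages (SAP 25.2.2.2), the registered denominator of the primary proportion (SAP 25.2.2.1) and the planned size (SAP 16: "A sample size of 30 has been estimated for this feasibility study"). The plan gives no event figures on this point, so there is none of its own to reproduce. Every event count below is an assumption chosen to show the mechanism.

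**Notation.** T = total SAEs; S = patients with at least one SAE; P = patients with a condition-specific AE and no SAE; N = 30 registered.

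- Planned SAE average = T / (S + P)
- SAEs per registered patient = T / N
- Primary proportion = (N − S − P) / N

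**Step 1: the SAE average is diluted by pain-only patients.**

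| T | S | P | Planned SAE average | SAEs per registered patient | Primary proportion |
|---|---|---|---|---|---|
| 2 | 2 | 0 | 2/2 = 1.00 | 2/30 = 0.067 | 28/30 = 93.3% |
| 2 | 2 | 8 | 2/10 = 0.20 | 0.067 | 20/30 = 66.7% |
| 2 | 2 | 13 | 2/15 = 0.13 | 0.067 | 15/30 = 50.0% |
| 4 | 3 | 0 | 4/3 = 1.33 | 4/30 = 0.13 | 27/30 = 90.0% |
| 4 | 3 | 6 | 4/9 = 0.44 | 0.13 | 21/30 = 70.0% |
| 4 | 3 | 12 | 4/15 = 0.27 | 0.13 | 15/30 = 50.0% |

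Within each block the SAEs are identical. Only the number of pain-only patients changes.

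**Step 2: the same happens in reverse.** Take 6 condition-specific AEs in 6 patients. With 0, 3 or 6 further patients who had only an SAE, the condition-specific average reads 6/6 = 1.00, 6/9 = 0.67 or 6/12 = 0.50.

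**Step 3: the patient count cannot be recovered from 25.2.2.2.** Take 9 affected patients, 4 SAEs and 8 condition-specific AEs, with no event counted as both. The outputs are 4/9 = 0.44, 8/9 = 0.89 and 12/9 = 1.33. These fit S = 1, 2, 3 or 4, that is 3.3%, 6.7%, 10.0% or 13.3% of 30. With S = 1, the other 8 patients have one pain event each. With S = 4, the other 5 have one each, and the remaining 3 pain events are repeats or fall in patients with an SAE. Fewer condition-specific AEs would narrow the range, because every affected patient without an SAE must have one.

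A wider contrast is 6 SAEs among 10 affected patients. The average is 6/10 = 0.60 whether one patient had all six (29/30 = 96.7% free of SAEs) or six had one each (24/30 = 80.0%).

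**Step 4: whether other outputs fill the gap.**

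- *SAP 26.* Four SAEs of four types, each in one patient, give four rows reading 1. That fits anything from 1 to 4 distinct patients. If the SAEs share a type, the row does give the patient count. SAP 26 therefore settles some cases only.
- *SAP 25.1.2.2.* This has the right format, but it serves the progression criteria and counts SARs rather than all SAEs. Its CRPS-pain item also carries a condition about the stopping of pain-related treatment that the primary outcome does not have.
- *Condition-specific AEs at final analysis.* The definitions include intensity and duration thresholds. SAP 26 does not say that its rows apply them.

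**The case against.** The case for leaving the text alone has several sound parts.

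- **Patient counts are not absent.** A reader might infer that the number of patients with an SAE is never shown. SAP 26 does not support that: it gives patients for each SAE type. What is missing is the total of distinct patients across types.
- **25.2.2.2 is not the only split.** A reader might also infer that these averages are the only separation of serious events from pain. SAP 26 covers serious and non-serious events by type, and SAP 25.1.2.2 separates SARs from each pain event at interim.
- **More pain events do not always lower the SAE average.** It falls only when they occur in patients who had no SAE. Repeat pain events, or pain in someone already counted, leave it unchanged.
- **Part of the distortion can be undone.** Total SAEs and the number registered are both reported, so SAEs per registered patient is one division away. The number of patients is not. That the combined average cannot fall below 1 is a property of any mean among affected patients and is no error.
- **The larger dilutions may be unlikely.** Thirteen of 30 is 43%, above the progression guide of at most 3 in the first 10. That guide is not a strict rule and uses a narrower CRPS-pain definition, and 8 of 30 (27%) already gives the fall from 1.00 to 0.20.
- **Table 3 should not be over-read.** It might suggest that an SAE-only proportion is the true primary outcome. The protocol's overview, objectives and outcome text, and SAP 15.1 and 25.2.2.1, all define the composite. Table 3 is at odds with them, and that inconsistency is a separate matter. Here it shows only that the protocol lists a patient-level SAE figure which the SAP does not produce.

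The study is also descriptive, tests no hypothesis, and has no progression criterion that uses these averages. All of this limits the size of the point. None of it supplies the missing patient counts.

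**Conclusion.** The point holds as a gap in how the components of the primary safety result are described. As written, the averages in SAP 25.2.2.2 mix the two components through their shared denominator. No final-analysis output gives the number of distinct patients with at least one SAE, or with at least one condition-specific AE.

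The primary proportion and the progression criteria are untouched. In the examples the SAE average moves about five- to sevenfold (1.00 to 0.20 or 0.13) with no change in SAEs, and one average fits 3.3% to 13.3% of patients having an SAE. These sizes rest on assumed event counts and on 30 registered. If few patients have any event, or if SAEs and pain fall in the same patients, the dilution is small. The missing patient totals remain in either case.

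This is worth changing before the final analysis because the summary is easy to misread and a correct one costs almost nothing.

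**What to change.** In SAP 25.2.2.2, replace the three averages with the number and percentage of participants who had:

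1. at least one SAE;
2. at least one injection-site pain event meeting the condition-specific definition;
3. at least one CRPS-pain event meeting that definition;
4. any of these.

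Use the registered denominator of SAP 25.2.2.1, so that the rows can be read against the primary proportion and row 4 is its complement. If any registered participant was not dosed, show the safety set of SAP 22.2 alongside. Keep the total event counts. If an average is still wanted, take it over all registered participants or over the patients with that component.

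The complement of row 1 also gives the measure listed in Protocol Table 3, so that needs no separate analysis.

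The cost is a few lines of SAP text and one small table. SAP 25.2.2.1 indicates that the event details are already collected on the adverse event and serious safety event forms.
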